### 10.3 – Secondary Endpoint #3

Endpoint Description: Tolerability measured as number of subjects developing hypotension (SBP  $\leq$  85 mmHg) with symptoms, using the pre-COVID-19 population.

Response Variable Definition: Number of subjects with a documented event of interest of symptomatic hypotension defined as systolic blood pressure  $\leq$  85 mmHg between Randomization and the Week 24 assessment.

Additional Covariates in Addition to Randomized Treatment: atrial fibrillation status at time of randomization

Handling of Dropouts and Missing Data: Each patient will be evaluated based on the available follow-up. No adjustment for incomplete follow-up will be made.

Sensitivity Analysis: Re-calculate the endpoint analysis using the original ITT population.

Statistical Tests: A logistic regression model (PROC LOGISTIC in SAS) will be used to estimate and statistically compare whether there is differential rate of subjects developing symptomatic hypotension between the treatments.

Interpretation of Results: A lower rate of symptomatic hypotension defined as systolic blood pressure  $\leq$  85 mmHg indicates better tolerance of LCZ696 arm versus Valsartan.

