16.2 Sample Size Justification and Randomization

Subjects will be randomized in a 1:1 allocation ratio using a permuted block design with stratification based on the clinical center and atrial fibrillation status. We plan to randomize 400 subjects with planned follow-up of 26 weeks. The primary efficacy endpoint is the proportional change from baseline in the AUC for NT-proBNP levels measured at 2, 4, 8, 12 and 24 weeks.

Based on recent Heart Failure Clinical Research Network (HFN) trials with similar follow-up requirements, we are anticipating a dropout / withdrawal of consent rate of approximately 5%. However, due to deaths and other sample collection issues we anticipate as many as 20-25% of subjects will not have NT-proBNP data at the week 24 assessment.

For the primary analysis, the AUC data will be log transformed and subjects missing the NT-proBNP data at the week 24 assessment will be assigned the last observation carried forward (LOCF). Based on a 2-sample t-test with type I error of 0.05 two-sided, the total sample size of 400 randomized subjects will provide 80% and 90% power to detect a differences of 19% and 21% for LCZ696 compared to valsartan. The PARAMOUNT phase II clinical trial observed a 23% greater reduction in NT-proBNP for LCZ696 compared to valsartan at 12 weeks post-randomization in patient population with HFpEF. ⁶ The HF Network investigators believe a 20% reduction in NT-proBNP would be considered a clinically significant improvement, and this level of change falls within a range considered clinically meaningful in a recent comparative effectiveness review published by AHRQ. ⁷

Sensitivity analyses will examine the influence of the imputation for the informatively missing data. For the complete case analysis, the total sample size of 400 subjects will provide approximately 80% and 95% power to detect reductions of 20% and 25% for LCZ696 compared to valsartan, respectively. These calculations were based on a two-sample t-test and assume that the standard deviation of the log-transformed 180-day AUC measure is 0.70. ⁸

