#### \* Analysis Modifications to Address COVID-19 Pandemic

The coronavirus COVID-19 pandemic has had a major impact on the performance of the LIFE trial. It was anticipated that patients will have greater difficulty attending study visits on their planned schedule due to restrictions on outpatient visits at many institutions. Therefore, patients will be unable to participate in study-related procedures such as biomarker sample collection, which comprises the primary endpoint for this trial. Additionally, due to restrictions on clinic access and potential concerns with patients going to the emergency department where exposure risk to COVID-19 is increased, we expect reporting of clinical endpoints such as emergency department visits and even hospital admissions to be impacted by the pandemic.

Therefore, due to the unexpected disruption brought on by the COVID-19 pandemic, the analysis plan was amended to restrict the reported program analyses to those patients that had their Week 12 visit prior to March 1, 2020, when the COVID-19 pandemic became more active in the continental United States. This translated to restricting the reported analyses to patients that were randomized on December 7, 2019 or earlier. Additionally, any study data collected after March 1, 2020 were excluded from the analyses for those patients randomized on or prior to December 7, 2019. This amended population will be labeled as the pre-COVID-19 population within the analysis plan.

The original protocol-specified analyses were to be conducted on all randomized patients using all available information. Those analyses will still be performed but will be considered to be sensitivity analyses.

Of the 365 patients randomized, 335 will be included in the pre-COVID-19 population. Twenty five of the 335 patients will have some visit information removed due to study visits occurring March 1, 2020 or later. The

remaining 30 patients will only contribute to the original protocol-specified analyses, now part of the sensitivity analyses.

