Not implanted with a LVAD: If a patient had been implanted with a LVAD, each day will be coded as a 0 if they were not implanted and will be coded as a 1 if the patient had been implanted. The last evaluable date will be minimum of 163 days post randomization, date of Week 24 visit, date of withdrawn consent, date of death or date of loss to follow-up.

Not maintained or starting continuous IV inotropes for at least 7 days: If the patient had been taking continuous IV inotropes for at least 7 days, each day from the start of inotropes (or randomization date if inotropes started prior to randomization) through the discontinuation of inotropes will be coded as a 1. If the patient does not have a discontinuation date, the assumption will be that inotropes continued to minimum of 163 days post randomization, date of Week 24 visit, date of withdrawn

consent, date of death, or date of loss to follow-up. For those days where the patient is not taking inotropes, the coded value will be 0.

Free of two heart failure hospitalizations: If the patient had two unplanned heart failure hospitalizations, each day from the second HF admission will be coded as a 1. Every day prior to the second HF admission will be coded as a 0. Coding will continue through a minimum of 163 days post randomization, date of Week 24 visit, date of withdrawn consent, date of death, or date of loss to follow-up.

Composite endpoint of event free days: Using each of the endpoint components above, determine the maximum value for the coded value for each of Day 0 through 163. If no endpoints met, the patient met the criteria for an event free day.

Additional Covariates in Addition to Randomized Treatment: atrial fibrillation status at time of randomization

Handling of Dropouts and Missing Data: To account for missing data due to right censoring, inverse probability weighted estimates will be calculated for each treatment group. These estimators adjust for the potential bias due to administratively censored data by reweighting the observed data by a function of the Kaplan-Meier estimate of the censoring distribution. The data will be partitioned from randomization (Day 0) to Day 79 and Day 80 to Day 163.

Sensitivity Analyses:

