## 11.6 – Tertiary Endpoint #6

Endpoint Description: Total number of unplanned heart failure hospital admissions through 24 weeks, using the pre-COVID-19 population.

Response Variable Definition: Number of unplanned heart failure hospitalizations between Randomization and Week 24.

Additional Covariates in Addition to Randomized Treatment: atrial fibrillation status at time of randomization

Handling of Dropouts and Missing Data: Each patient will be evaluated based on the available follow-up. No adjustment for incomplete follow-up will be made.

Sensitivity Analysis: Re-calculate the endpoint analysis using the original ITT population.

Statistical Tests: A Poisson regression model (PROC GENMOD in SAS) will be used to estimate and statistically compare whether there is differential rate of subjects experiencing unplanned heart failure hospital admissions between the treatments.

Interpretation of Results: A smaller number of unplanned heart failure hospitalizations through 24 weeks indicates a reduction in admissions in the LCZ696 arm versus Valsartan.

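### SAP 11.6 compares heart-failure admission rates without a follow-up offset, and six yes/no endpoints score patients who leave early as non-events; the bias is modest and needs follow-up to differ by arm

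*SAP*

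**What the plan says.** SAP 10.3 (symptomatic hypotension) counts subjects with the event "between Randomization and the Week 24 assessment" and states: "A logistic regression model (PROC LOGISTIC in SAS) will be used to estimate and statistically compare whether there is differential rate of subjects developing" that event. SAP 10.4 (eGFR below 20) and 10.5 (hyperkalaemia) do the same. SAP 11.7 (inotropes), 11.8 (transplant listing, transplant or LVAD) and 11.11 (unanticipated IV diuretics) also use logistic regression on an event through Week 24.

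For the number of heart-failure admissions, SAP 11.6 states: "A Poisson regression model (PROC GENMOD in SAS) will be used to estimate and statistically compare" whether the admission rate differs between treatments.

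In all seven sections the only covariate besides treatment is "atrial fibrillation status at time of randomization". No offset is named, no rule removes early leavers, and the missing-data entry is: "Each patient will be evaluated based on the available follow-up. No adjustment for incomplete follow-up will be made".

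Two other parts of the SAP do deal with incomplete follow-up. SAP 11.1 to 11.5 carry the same sentence, but there a Cox model censors at last follow-up. SAP 10.1 says: "To account for missing data due to right censoring, inverse probability weighted estimates will be calculated for each treatment group".

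On how much follow-up will be missing, Protocol 16.2 says "we are anticipating a dropout / withdrawal of consent rate of approximately 5" per cent. The COVID-19 text in SAP 3 adds: "Twenty five of the 335 patients will have some visit information removed due to study visits occurring March 1, 2020 or later". Stopping study drug does not by itself end follow-up, because Protocol 12.2 keeps those patients in assessment through Visit 11.

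**The concern.** A rate needs a denominator in time. Without an offset, the Poisson model in 11.6 gives a patient followed for two weeks and a patient followed for 24 weeks the same exposure. Admissions before exit count; the shortened time at risk does not.

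In the six logistic analyses, a patient who withdraws in week 2 with no event so far is recorded exactly like one observed event-free for 24 weeks. A patient whose event came before exit is still counted, so the misclassification is confined to those who leave without one.

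Each section reads a lower figure as better tolerance or improvement on LCZ696. If exits are more frequent or earlier in one arm, that arm gains from its shorter observation. Three of the four tolerability secondaries (10.3, 10.4, 10.5) are affected, and nothing in the planned output shows the reader how much follow-up each arm contributed.

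**Working it through.** **Inputs from the documents.** 24-week window; about 5% withdrawal (Protocol 16.2); 335 patients in the pre-COVID-19 population, 25 of them truncated (SAP 3); latest randomization date 7 December 2019 (SAP 3). An 18% hypotension risk is borrowed for illustration from the enalapril-controlled trial described in Protocol 11.6.

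**Assumptions.** Constant, independent hazards. Mortality and withdrawal by arm are not in the documents and are varied below.

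**The plan's own figures.** None is given for these seven endpoints. The nearest is the power for death or first heart-failure readmission (Protocol 16.2): 88% for 40% vs 25% and 55% for 40% vs 30%, with 200 per arm. Power = Φ[(|p1−p2|√n − 1.96√(2p̄(1−p̄))) / √(p1(1−p1)+p2(1−p2))].
- 40% vs 25%: (2.121 − 1.298)/0.654 = 1.259, so 89.6%.
- 40% vs 30%: (1.414 − 1.322)/0.671 = 0.137, so 55.5%.

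Both agree with the plan to within 2 points, but say nothing about follow-up.

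**Step 1: counts without an offset (SAP 11.6).** With 24-week mortality d, H = −ln(1−d) and the mean fraction of 24 weeks observed is (1−e^−H)/H = d/H.

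| Mortality | H | Fraction observed | Weeks |
|---|---|---|---|
| 10% | 0.1054 | 0.9491 | 22.78 |
| 15% | 0.1625 | 0.9230 | 22.15 |
| 20% | 0.2231 | 0.8963 | 21.51 |

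At equal true admission rates, the ratio without an offset is the ratio of mean follow-up.
- 20% vs 10%: 0.8963/0.9491 = 0.944.
- 15% vs 10%: 0.9230/0.9491 = 0.972.
- Equal mortality: 1.00.

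A true ratio of 0.75 in favour of the arm with 10% mortality, against 20%, appears as 0.75/0.944 = 0.79. Adding 5% withdrawal to both arms gives mean follow-up of 22.21, 21.61 and 20.99 weeks, and ratios of 20.99/22.21 = 0.945 and 21.61/22.21 = 0.973.

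**Step 2: withdrawal in the yes/no endpoints.** With event hazard h = −ln(1−0.18) = 0.19845 and total exit hazard L, the crude proportion is h/(h+L) × (1−e^−(h+L)). Take 10% mortality in both arms (hazard 0.10536).
- No withdrawal, which is the cumulative incidence with death competing: 0.19845/0.30381 × 0.2620 = 17.1%.
- 5% withdrawal (adds 0.05129): 0.19845/0.35510 × 0.2989 = 16.7%.
- 10% withdrawal (assumed; adds 0.10536): 0.19845/0.40917 × 0.3358 = 16.3%.

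With 5% withdrawal in both arms, each is understated by 0.4 points and the odds ratio is 1.00. With 10% vs 5%, the odds ratio is (0.1629/0.8371)/(0.1670/0.8330) = 0.97 with no true effect.

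**Step 3: the 1 March 2020 cut.** 7 December 2019 plus 84 days is 29 February 2020, so every truncated patient keeps about 12 weeks. 25/335 = 7.5% of patients are affected. The most person-time that can be lost is 25×12/(335×24) = 3.7%; at an assumed average loss of 6 weeks it is 1.9%. The cut follows the calendar, not the arm.

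**The case against.** The strongest reply concerns death. The proportion with an event by Week 24, counting patients who died without it as non-events, is a legitimate cumulative incidence with death as a competing event. The protocol words these endpoints as numbers of subjects, which fits. A Cox model censoring at death would target a cause-specific hazard, a different quantity, and could not be called a correction. This stands for the six yes/no endpoints. A similar defence of 11.6 as a mean count is weaker, because that section says it compares a rate. The defence does not reach withdrawal, loss to follow-up or the data cut, which are plain censoring.

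SAP 10.1 might be read as showing that the plan corrects for death elsewhere and forgot to do so here. It does not. In 10.1 days after death are scored as event days, and the weighting is for administrative censoring. The contrast holds only for exits other than death.

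The size is also fairly challenged. Mortality of 20% vs 10% implies a hazard ratio of 0.1054/0.2231 = 0.47. The only mortality effect in the protocol is 0.84 (section 6, another population and comparator). Applied to an assumed 20% control mortality it gives 17.1%, and a count ratio of 0.8963/0.9119 = 0.983. Even at 20% vs 10%, with 335 patients and 18% risk, the distortion of a crude proportion is about 0.9 percentage points, or 0.23 standard errors of the log odds ratio. If events cluster around the titration visits at weeks 2 and 4, it is smaller still.

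Finally, every one of the seven analyses is repeated in the original ITT population, which restores the data after 1 March 2020. That disposes of the cut as a serious source of bias; it does nothing for withdrawal or loss. Deaths are also reported in their own right (SAP 11.1, 11.4 and 12.1).

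**Conclusion.** The point holds in a limited form. SAP 11.6 sets out to compare a rate and ignores time at risk. The six logistic endpoints leave censoring from withdrawal, loss and the data cut uncorrected. The arm with shorter follow-up would look somewhat better than it is: a count ratio of 0.944 to 0.983 in place of 1.00 over the mortality differences examined, and an odds ratio of about 0.97 if withdrawal were 10% vs 5%. These figures rest on constant hazards and on assumed exits by arm.

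A reader might infer that the arm with more deaths will look better tolerated than the other. The documents do not support that. They report no deaths by arm; with equal exits there is no false difference; and a truly worse arm still looks worse. For example, true hypotension risks of 18% vs 12% with deaths of 20% vs 10% and 5% withdrawal would appear as 15.8% vs 11.1%, an odds ratio of 1.50 instead of 1.61. Nor can the 1 March 2020 cut carry the argument: it is small, unrelated to arm and undone in the ITT repeat.

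**What to change.** 1. In SAP 11.6, add an offset of log(days from randomization to the earliest of Week 24, death, withdrawal, last contact and, in the pre-COVID-19 population, 1 March 2020). Delete the no-adjustment sentence there.
2. For SAP 10.3, 10.4, 10.5, 11.7, 11.8 and 11.11, keep the crude counts and the logistic model. Add a 24-week cumulative incidence by arm that treats death as a competing event and censors at withdrawal, loss to follow-up or the data cut. In 11.7, start time at randomization, or at index discharge if later. In 11.7 and 11.8, count patients already in the state at time zero separately; eligibility allows chronic inotropes and excludes listed patients only if hospitalized.
3. Tabulate deaths, withdrawals and follow-up time by arm beside the tolerability results.

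**Cost.** The offset is one term in an existing model. The cumulative incidence needs event dates; SAP 10.1 already uses those for admissions, inotropes, listing, transplant and LVAD, while laboratory events are dated only to the visit at which they were found. The 11.6 result becomes a rate ratio per unit of follow-up while alive, and should be labelled so.

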#### **10.4 – Secondary Endpoint #4**

Endpoint Description: Tolerability measured as number of subjects developing worsening renal function (eGFR <20 ml/min/1.73m^2), using the pre-COVID-19 population.

Response Variable Definition: Number of subjects with a documented event of interest of worsening renal function defined as eGFR <20 ml/min/1.73m^2 between Randomization and the Week 24 assessment.

Additional Covariates in Addition to Randomized Treatment: atrial fibrillation status at time of randomization

Handling of Dropouts and Missing Data: Each patient will be evaluated based on the available follow-up. No adjustment for incomplete follow-up will be made.

Sensitivity Analysis: Re-calculate the endpoint analysis using the original ITT population.

Statistical Tests: A logistic regression model (PROC LOGISTIC in SAS) will be used to estimate and statistically compare whether there is differential rate of subjects developing worsening renal function between the treatments.

Interpretation of Results: A lower rate of developing worsening renal function defined as GFR < 20 ml/min/1.73m^2, indicates better tolerance of LCZ696 arm versus Valsartan.

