7.3 Study Intervention Phase

Study treatment will be titrated to the target dose of 200 mg LCZ696 (equivalent to Entresto™ 97/103 mg) as two 100 mg LCZ696 and 2 placebo tablets po BID or valsartan 160 mg (two 80 mg valsartan and 2 placebo tablets) po BID.* Randomized subjects will receive the first dose of study drug as follows:

[figure not shown]
- For subjects not previously taking ACEI or ARB, previously taking ACEI or ARB at a low dose*, or subjects who have an eGFR < 30 mL/min/1.73m², the starting dose of valsartan will be 40 mg po BID and the starting dose of LCZ696 will be 50 mg po BID.
- For subjects taking an ARB at greater than low dose†, the starting dose of valsartan will be 80 mg po BID and the starting dose of LCZ696 will be 100 mg po BID.
- For subjects taking an ACEI at greater than low dose†, the ACEI will be withheld for ≥ 36 hours prior to randomization. The starting dose of valsartan will be 80 mg po BID and the starting dose of LCZ696 will be 100 mg po BID.

* Per package insert, the valsartan compounded in Entresto™ is more bioavailable than the valsartan in other marketed formulations. The dose equivalence for valsartan compounded in Entresto™ compared to valsartan prepared alone (Entresto™ dose = marketed valsartan dose) is as follows: 26 mg=40 mg, 51 mg=80 mg, 103 mg=160 mg.

† Low dose is defined as 24 hour dose of ≤ 10 mg lisinopril, ≤ 5 mg ramipril, ≤ 50 mg losartan, ≤ 10 mg olmesartan, or other dose equivalent.

Dose adjustments will be performed every 2 weeks by doubling the dose of LCZ696 or valsartan up to the target maximum dose. The doses of LCZ696 are 50 mg (one 50 mg active and 1 placebo tablet), 100 mg (one 100 mg active and 1 placebo tablet) and 200 mg (two 100 mg active and 2 placebo tablets). These doses are equivalent to 24/26 mg, 49/51 mg, and 97/103 mg commercial Entresto™, respectively. The doses of valsartan are 40mg (one 40 mg active and 1 placebo tablet), 80 mg (one 80 mg active and 1 placebo tablet), and 160 mg (two 80 mg active and 2 placebo tablets). The criteria for doubling the dose will be based on systolic blood pressure (a SBP > 90 mmHg is required for up titration), changes in renal function (maximum serum creatinine of 2.0 mg/dL), and the absence of symptoms of hypotension. For those not tolerating the current dose of study drug, the dose will be down-titrated to the previous tolerated dose. Subjects will return to clinic for follow-up visits at 2, 4, 8, 12, 24 and 26 weeks after randomization.

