9.3 Exclusion Criteria

1. Currently taking Entresto™
2. History of hypersensitivity or intolerance (unmodifiable) to Entresto™, an ACEI or ARB as well as known or suspected contraindications (including hereditary angioedema) to the study drugs.
3. Estimated glomerular filtration rate (eGFR) < 20 mL/min/1.73 m² at baseline
4. Co-morbid conditions that may interfere with completing the study protocol (e.g. recent history of drug or alcohol abuse) or cause death within 1 year
5. Symptomatic hypotension at randomization or systolic blood pressure < 90 mmHg
6. Serum potassium > 5.5 mmol/L
7. Severe liver dysfunction (Childs-Pugh Class C)
8. Acute coronary syndrome within 4 weeks as defined by electrocardiographic (ECG) changes and biomarkers of myocardial necrosis (e.g. troponin) in an appropriate clinical setting (chest discomfort or anginal equivalent)
9. Planned or recent (≤ 4 weeks) PCI, coronary artery bypass grafting, or biventricular pacing
10. Currently hospitalized and listed status 1A, 1B or 1-4 for heart transplant
11. Current or scheduled for LVAD implantation within 30 days of study enrollment
12. Active infection (current use of oral or IV antimicrobial agents)
13. Primary hypertrophic or infiltrative cardiomyopathy, acute myocarditis, constrictive pericarditis or tamponade
14. Complex congenital heart disease
15. Concomitant use of aliskiren in patients with diabetes or renal impairment (eGFR < 60 mL/min/1.73 m²)
16. Known pregnancy or anticipated pregnancy within the next 6 months or breastfeeding mothers
17. Enrollment in any other investigational clinical trial within 30 days prior to screening
18. Inability to comply with study procedures

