13.2 Secondary Endpoints

1. Days alive and out of hospital at 6 months, not listed for transplant (status 1A, 1B or 1-4) or undergoing transplant, implanted with an LVAD, maintained or started on continuous inotropic therapy for ≥ 7 days, or has had two hospital admissions for HF (other than the index admission*). If a patient meets the pre-specified secondary endpoint of 2 hospital admissions for heart failure (other than the index admission), the patient can remain on study drug or be started on open label sacubitril/valsartan, at the treating physician's discretion, while remaining in the trial.

*The days alive and out of hospital will end on the day of the second readmission.

2. Tolerability measured as:
 - a) Number of subjects achieving a target dose of 25%, 50% or 100% of valsartan or LCZ696
 - b) Number of subjects developing hypotension (SBP ≤ 85 mmHg) with symptoms
 - c) Number of subjects developing worsening renal function (eGFR < 20 ml/min/1.73 m²)
 - d) Number of subjects developing moderate (≥ 5.5 mmol/L) or severe (≥ 6 mmol/L) hyperkalemia

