### 2.2 Randomization

Patients are randomized in a 1:1 ratio to either LCZ696 + Valsartan-placebo or Valsartan + LCZ696-placebo. The randomization scheme consists of a permuted block design with stratification by clinical site and atrial fibrillation status.

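### SAP 10.4 models falling below eGFR 20, in patients enrolled down to eGFR 20, without baseline eGFR: valid on average, but it gives up precision and leaves chance imbalance uncorrected

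*SAP*

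**What the plan says.** Protocol 13.2 lists among the tolerability endpoints "Number of subjects developing worsening renal function", with the cut at eGFR below 20. SAP 10.4 turns this into a yes/no outcome between randomization and Week 24: a "documented event of interest of worsening renal function defined as eGFR <20". The test for this renal outcome is specified as "A logistic regression model (PROC LOGISTIC in SAS) will be used to estimate and statistically compare whether there is differential rate of subjects developing worsening" (the sentence then completes the endpoint's name). The covariate line reads "Additional Covariates in Addition to Randomized Treatment: atrial fibrillation status at time of randomization", and the only sensitivity analysis is a re-run in the original ITT population.

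Protocol 9.3 excludes "Estimated glomerular filtration rate (eGFR) < 20 mL/min/1.73 m² at baseline", so a patient at 20 or just above may enter. The protocol expects some patients near that floor, since Protocol 7.3 has a starting-dose category that includes "subjects who have an eGFR < 30 mL/min/1.73m²". SAP 2.2 describes "stratification by clinical site and atrial fibrillation status", so renal function is not balanced by design. SAP 15 names no renal subgroup.

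Creatinine is measured at Visit 2, before the first randomized dose (Protocol 12.1). The SAP adjusts for the outcome's own baseline in the primary analysis (SAP 9.1), the KCCQ analysis (SAP 11.12) and the NT-proBNP/BNP analysis (SAP 11.13).

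**The concern.** With an absolute cut placed at the entry limit, how far a patient must deteriorate depends on where that patient started. Baseline eGFR is therefore expected to be a strong predictor of the event, yet the model leaves it out.

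Two things follow. A strong predictor left out of a logistic model makes a real treatment difference harder to detect. And if one arm happens to receive more patients close to 20, the odds ratio moves for a reason unrelated to treatment, with nothing in the model to take that out.

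Both matter because tolerability is a stated secondary objective. Protocol 11.6 says the risks of LCZ696 in advanced heart failure with lower blood pressure are unknown, and SAP 10.4 reads a lower rate directly as better tolerance of LCZ696.

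**Working it through.** **Inputs from the documents.** Event: eGFR below 20. Entry: eGFR 20 or above. Analysis set: 335 (SAP 3), allocated 1:1 (SAP 2.2), so 335/2 = 167.5 per arm. Tests: two-sided at 0.05 (SAP 4).

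**Assumed inputs (not in the documents).** Baseline eGFR is normal, truncated at 20, with mean/SD 55/20 or 65/22. Atrial fibrillation prevalence is 40%. Lowest on-study log eGFR = log baseline − drift − treatment shift + normal error. Drift is 0.15 or 0.25, error SD 0.30 or 0.40, and shift 0 or 0.20.

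**1. Distance to the cut.** Required fall = (baseline − 20)/baseline. From 22 it is 2/22 = 9.1%. From 70 it is 50/70 = 71.4%.

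**2. Size of chance imbalance.** If a share p of patients has baseline eGFR 20 to 30, the 95% range for the difference between arms is ±1.96 × √(2p(1−p)/167.5).
- p = 5%: 1.96 × √(0.095/167.5) = ±4.7 points.
- p = 15%: 1.96 × √(0.255/167.5) = ±7.6 points.

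**3. Benchmark.** The plan gives no power for this endpoint, so there is no figure to reproduce. The normal-approximation formula for two proportions was checked on the protocol's one binary power statement (Protocol 16.2: 88% for 40% vs 25%, 55% for 40% vs 30%). It gives 89.6% and 55.5% at 200 per arm, within 2 points. The formula is power = Φ{[|p1−p2| − 1.96√(2p̄(1−p̄)/n)] / √[(p1(1−p1)+p2(1−p2))/n]}. For 5% vs 10% at n = 167 it is Φ{(0.0500 − 0.0565)/0.0287} = 41.0%, and for 4% vs 9% it is 45.7%. Even before the covariate question, this endpoint has limited power.

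**4. Simulation with every crossing captured** (2,000 trials per row, Wald test). Power is at shift 0.20. The odds ratios (OR) are medians under no effect, in the tenth of trials where the LCZ696 arm drew the lowest relative baseline eGFR.

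| Baseline mean/SD | Error SD, drift | Events, valsartan vs LCZ696 | Power, AF only | Power, + log baseline eGFR | Gain (points) | Null OR, AF only | Null OR, adjusted |
|---|---|---|---|---|---|---|---|
| 55/20 | 0.30, 0.15 | 4.2% vs 8.9% | 39.6% | 56.8% | 17.2 | 1.51 | 1.04 |
| 55/20 | 0.40, 0.25 | 8.5% vs 15.6% | 51.0% | 64.4% | 13.4 | 1.38 | 1.04 |
| 65/22 | 0.30, 0.15 | 2.3% vs 5.1% | 18.6% | 32.8% | 14.2 | 1.63 | 1.08 |
| 65/22 | 0.40, 0.25 | 5.2% vs 9.9% | 35.6% | 45.6% | 10.0 | 1.42 | 0.98 |

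Over all null trials the AF-only test rejected in 1.0% to 5.2%, and the adjusted test in 1.8% to 5.8%.

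**5. Simulation with imperfect capture or a smaller effect** (167 per arm, baseline 55/20, drift 0.15; error SD 0.35 and shift 0.20 unless stated; 1,200 trials per row). The capture rates are also assumed. A repeat with a different seed agreed within about 2 points.

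| Scenario | Power, AF only | Power, + log baseline eGFR |
|---|---|---|
| All crossings captured | 42% | 55% |
| 50% captured | 16% | 21% |
| 60% captured, plus 2% unrelated reports | 19% | 21% |
| Error SD 0.60, all captured | 38% | 43% |
| Error SD 0.60, 60% captured, plus 2% unrelated | 18.6% | 18.9% |
| Half the effect, all captured | 13% | 17% |

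**The case against.** The strongest defence is that nothing is invalid. Treatment is randomized, atrial fibrillation is adjusted for, and chance imbalance in baseline eGFR is already part of the test's error rate. That stands. A reader might infer that the planned comparison is biased, or that an imbalance will show up as a renal drug effect. The documents do not support that. The shifted odds ratios in step 4 arise only after selecting the trials with the worst imbalance; they are not an expected bias.

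A reader might also take the 10 to 17 points as the gain to expect. That does not stand either. SAP 10.4 counts site-documented events of interest, and Protocol 15.9 describes worsening renal function differently: typically a fall of at least 20% over 48 hours, or progressive loss. Recorded events may therefore not track threshold crossing closely, and step 5 shows the gain then shrinking, in one case to almost nothing. Noisy capture would shrink the odds-ratio shift as well.

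Renal change from the patient's own baseline is analysed elsewhere, for eGFR (SAP 11.9) and cystatin C (SAP 11.10), so the count below 20 would not be read alone. That limits the consequence. It does not repair the estimate in SAP 10.4, which has its own test and its own interpretation line.

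Finally, events may be few: about 12 to 26 in the error-SD-0.35 setup. That is a reason for a penalized fallback, not for leaving out a single continuous predictor.

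**Conclusion.** The point holds as a matter of efficiency and of accuracy in the trial actually drawn. The documents confirm that the cut coincides with the entry floor, that renal function is not a stratification factor, and that baseline eGFR is obtainable but missing from the model. The planned test keeps its error rate.

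The power gain lies between about 0 and 17 points. The upper part of that range requires complete capture and a log-scale shift of 0.20. The odds-ratio shift of about 1.4 to 1.6 also assumes complete capture and applies only to a minority of trials. Every magnitude depends on an assumed eGFR distribution, event rate and effect. In most scenarios power stays modest even after adjustment, so the change improves this endpoint without making it decisive.

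For potassium (SAP 10.5) the structure is similar: Protocol 9.3 excludes values above 5.5 mmol/L and the SAP counts values above 5.5. A reader might infer an equal gain from adjusting for baseline potassium. None has been quantified, and how well baseline potassium predicts the event is unknown.

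**What to change.** Before unblinding, add one continuous term to the Secondary #4 logistic model: log baseline eGFR from Visit 2. Name that visit in the SAP. It is the last value before randomized drug and, unlike Visit 0, it follows the LCZ696 run-in that both arms share. Keep atrial fibrillation and the endpoint definition. Pre-specify a Firth-penalized fit if events are sparse, with the event count that triggers it. Report counts, percentages and the crude risk difference by arm beside the odds ratio.

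Baseline potassium may be added to Secondary #5 on the structural argument alone. Separately, the descriptions of worsening renal function in Protocol 15.9 and SAP 10.4 should be reconciled, because they determine which events are recorded.

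The cost is one covariate from data already collected. The adjusted odds ratio is conditional on baseline eGFR and can differ from the unadjusted one even without imbalance, so it must be labelled as conditional.
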